5.2 Exclusion Criteria

Patients are excluded from the trial if any of the following criteria apply:

- 1. Acute deep vein thrombosis or clinically relevant pulmonary embolism, not stable for at least 8 weeks prior to first IMP administration.
- 2. Have clinically significant cardiac disease, including:
 - Onset of unstable angina up to six months prior to signing the ICF.
 - Acute myocardial infarction up to six months prior to signing the ICF.
 - Known congestive heart failure (Grade III or IV as classified by the New York Heart Association); and/ or a known decreased cardiac ejection fraction of < 45%.
 - A baseline QT interval as corrected by Fridericia's formula (QTcF) > 480 msec or a complete left bundle branch block (defined as a QRS interval ≥ 120 msec in left bundle branch block form).
- 3. Uncontrolled hypertension defined as systolic blood pressure ≥160 mmHg and/or diastolic blood pressure ≥100 mmHg, despite optimal medical management.

- 4. Any history of intracerebral arteriovenous malformation, cerebral aneurysm, new (younger than 6 months) or progressive brain metastases or stroke.
 - Transient ischemic attack > 1 month prior to screening is allowed.
 - Patients with a history of symptomatic metastatic brain or meningeal tumors may be included, if the end of definitive therapy is > 6 months before the first dose of trial drug and the patient is having clinically or radiologically no evidence of tumor growth. Patients with brain metastases must not be undergoing acute corticosteroid therapy or steroid taper. Chronic steroid therapy is acceptable provided that the dose is stable for the last 14 days prior to screening.
 - Patients with central nervous system symptoms should undergo a Computed Tomography (CT) scan or Magnetic Resonance Imaging of the brain to exclude new or progressive brain metastases. Spinal cord metastasis is acceptable. However, patients with spinal cord compression should be excluded.
- 5. History of chronic liver disease or evidence of hepatic cirrhosis.
- 6. History of organ allograft (except for corneal transplant) or autologous or allogeneic bone marrow transplant, or stem cell rescue within 3 months prior to the first dose of IMP.
- 7. Have received granulocyte colony stimulating factor (G-CSF) or granulocyte/macrophage colony stimulating factor support 4 weeks prior to first IMP administration or being chronically transfusion dependent.
- 8. Have received a cumulative dose of corticosteroid \geq 150 mg prednisone (or equivalent doses of corticosteroids) within two weeks before the first IMP administration.
- 9. History of \geq grade 3 allergic reactions to monoclonal antibody therapy as well as known or suspected allergy or intolerance to any agent given in the course of this trial.
- 10. Radiotherapy within 14 days prior to first IMP administration. (Palliative radiotherapy will be allowed as described in Section 6.4.2).
- 11. Any anticancer therapy (including: small molecules, immunotherapy, chemotherapy monoclonal antibodies or any other experimental drug) given within five half-lives before first infusion.
 - For anti-cancer therapies with half-lives greater than 5.5 days, a washout period of at least four weeks is acceptable (six weeks for nitrosureas or mitomycin).

Accepted exceptions are bisphosphonates (e.g. pamidronate, zoledronic acid, etc.) and denosumab.

- Toxic effects of prior anti-cancer therapy considered as chronic, such as chemotherapy-induced fatigue, alopecia, or anorexia of \leq grade 2, where anymore resolution is not expected, does not prevent the patient from participation in the trial.
- 12. Any prior therapy with a compound targeting DR4 or DR5.
- 13. Known past or current malignancy other than inclusion diagnosis, except for:
 - Cervical carcinoma of Stage 1B or less.
 - Non-invasive basal cell or squamous cell skin carcinoma.
 - Non-invasive, superficial bladder cancer.

- Prostate cancer with a current PSA level < 0.1 ng/mL.
- Any curable cancer with a complete response (CR) of > 2 years duration.
- 14. Known human immunodeficiency virus seropositivity.
- 15. Known history / positive serology for hepatitis B (unless immune due to vaccination or resolved natural infection or unless passive immunization due to immunoglobulin therapy):
 - Positive test for antibodies to hepatitis B core antigens (anti-HBc)

and

- Negative test for antibodies to hepatitis B surface antigens (anti-HBs).
- 16. Known history / positive serology for hepatitis C (unless due to immunoglobulin therapy), which has not been cured.
- 17. Ongoing significant, uncontrolled medical condition including:
 - Serious, non-healing wound, skin ulcer (of any grade), or bone fracture.
- 18. Clinically significant active viral, bacterial or fungal infection requiring:
 - Intravenous treatment with anti-infective therapy that has been administered less than two weeks prior to first dose.
- 19. Substance abuse, medical, psychological or social conditions that may interfere with the patient's participation in the trial or evaluation of the trial result.

5.3 Screen Failures

Screen failures are defined as patients who consent to participate in the clinical trial but are not subsequently entered in the trial. A minimal set of screen failure information is required to ensure transparent reporting of screen failure patients to meet the Consolidated Standards of Reporting Trials (CONSORT) publishing requirements and to respond to queries from regulatory authorities. Minimal information includes demography, screen failure details, eligibility criteria, and any serious adverse event.

Individuals who do not meet the criteria for participation in this trial (screen failure) may be rescreened once only. The rescreening must be approved by the sponsor to ensure that the safety of the patient is not compromised.

If rescreening is approved, complete new screening must be performed and all eligibility criteria must be re-assessed. If more than 4 weeks have passed since the initial screening failed the patient must be re-consented. Also a new ICF should be signed if updates have been made since signing of the first ICF.

6 TREATMENT

6.1 Treatment Assignment

6.1.1 Patient Numbering

After obtaining informed consent, patients will be given a screening number before they undergo any screening procedure. A screening ID consists of the letter "S" followed by a three-digit sequence number that uniquely identifies a patient at a screening visit e.g. S004.

When screening has been completed and the patient satisfies the eligibility criteria, the patient is given a patient ID. A patient ID consists of a four-digit number that uniquely identifies a patient, e.g., patient 0012.

6.1.2 Treatment Assignment

This is an open-label trial; therefore, blinding of treatment will not be performed. Allocation of patients will be controlled by the CRO.

Escalation Part:

When a potential patient in the dose escalation is identified at a site, the site personnel must contact the CRO for allocation in accordance to Section 4.3. If there is an opening in the currently enrolling cohort, the site will be given approval to start the screening process. If there is no opening in the currently enrolling cohort, the CRO will place the patient on a list of potential patients. If another patient fails the screening process, the CRO will alert the site that has the next patient on the waiting list. If the patient is still eligible, the site will be given approval to start the screening process.

Expansion Part:

In the expansion part, treatment assignment will be done through an electronic system, for example, the interactive response technology (IRT) system. The CRO will oversee the recruitment and notify the sites when cohorts are complete. If only one dose regimen is opened within an indication, eligible patients will be allocated to this. In the situation where more than one dose regimen is available to eligible patients within an indication, patients will be allocated as follows to available regimens:

- If two dose regimens are available within the indication, patients will be randomized in a 1:1 fashion, stratified by ECOG score at screening
- Should one dose regimen within an indication be stopped during the expansion phase, the allocation mechanism will switch to allocation into the one regimen left.

6.2 Dosage and Administration

GEN1029 should be diluted into a 0.9% NaCl (saline) 100 mL (or 250 mL dependent on total dose) infusion bag according to the dose assigned to the patient and administered within 24 hours of preparation.

GEN1029 should be administered intravenously over a minimum of 60 minutes and the infusion must be completed within 90 minutes using a 0.2 μ m in-line filter. The entire infusion volume from the prepared infusion bag needs to be administered, no dead volume is provided. The infusion is complete when the infusion line has been flushed with minimum 15 mL saline.

The dose will be calculated based on the patient's weight rounded to the nearest kilogram, i.e., assigned cohort dose in mg/kg x body weight in kg.

For patients whose body mass index (BMI) is greater than 30 kg/m^2 , the investigator should use a weight that, based on the patient's height, corresponds to a maximum BMI of 30.

Please refer to the IMP manual for dose calculation and additional information regarding IMP administration.

6.3 Compliance

Trial drug will be administered by site personnel to assure compliance with trial requirements. The date and time of each trial drug administration will be recorded in the eCRF.

6.4 Concomitant Medications and Therapies

Any medication or vaccine (including over-the-counter or prescription medicines, vitamins, and/or herbal supplements) other than GEN1029 the patient is receiving at the time of enrollment or receives during the trial must be recorded along with:

- Reason for use
- Dates of administration including start and end dates
- Dosage information including route, dose and frequency

The patient must be told to notify the investigational site about any new medications he or she takes after the start of the trial drug.

The Medical Monitor should be contacted if there are any questions regarding concomitant or prior therapy.

6.4.1 Prophylactic Concomitant Medication

Fourteen out of 27 patients (11 out of 24 patients in the Biweekly Regimen and 3 out of 3 patients in the Intensified Regimen) have experienced transaminase elevations \geq grade 2. These elevations seem to be primarily a first-dose effect, and independent of dose level or presence of liver metastasis. Preliminary data from the ongoing dose escalation suggests that pre-medication with steroids may prevent elevations of transaminases.

Therefore, mandatory pre-medication with Dexamethasone must be administered as follows:

- 4 mg/p.o. one day before dosing at Cycles 1 and 2.
- Dose escalation part: 10 mg. i.v. at Day 1 before dosing and at Day 2 in Cycles 1 and 2. Expansion part: 10 mg. i.v. at Day 1 before dosing and orally at Day 2 in Cycles 1 and 2.

If a drug-related \geq grade 2 elevation of ALT and/or AST is observed during the second cycle or thereafter, dexamethasone pre-medication should be continued/re-introduced. In this case, Dexamethasone can be given orally on the day after the dosing day.

Furthermore, the below guidance should be followed throughout the trial:

• Paracetamol (Acetaminophen) and antihistamines (Diphenhydramine, 50 mg p.o. preferred, or Dexchlorpheniramine (5 mg i.v.), can be part of the pre-medication regimen as judged necessary by the investigator.

All pre-medication must be reported on the concomitant medication page in the eCRF.

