²² The day 8 visit can be omitted after approval by the sponsor medical monitor if there have been no AEs fulfilling the DLT criteria in the previous 6 cycles.
²³ To be completed as indicated to confirm response, new symptoms, end of treatment visit or at the physician discretion, see Section 9.2.
²⁴ Cytokine, complement and PK sampling to be taken at Cycles 1 and 2 Day 3 after infusion, see Table 1-3 and Table 1-4.
²⁵ A complete general physical examination will be done at the screening and Cycle 1 Day 1 visits. At subsequent visits and as clinically indicated limited symptom-directed physical examinations should be
performed.
26 Any AST, ALT, and/or bilirubin > grade 2 needs to be checked 2×/week for up to 4 weeks and until resolution or return to baseline.
27 Reneat at least once more, i.e. on Day 5 if AST, ALT, or bilinibin > grade 1 and > 1.5×baseline.
28 If no AST. ALT. and/or bilimbin > grade 2 elevations are observed in Cycle 1 and 2, the visit at Cycle 3 Day 3 can be omitted
²⁹ The PET must be combined with CT and the CT portion must be of similar diagnostic quality to CT alone. The PET-CT must be performed before any optional tumor biopsy to avoid potential false positive
findings. The baseline PET-CT assessment during screening should be performed at the closest date as possible from start of trial treatment, at least one week before tumor bionsy. Of note, if tumor leasons
showed no avidity at baseline, no further PET scans should be performed, but CT scans only.
³⁰ To be performed only if a patient, who has been exposed to GEN1029, did not have any PET-CT scans while on treatment and displayed avidity at screening.
³³ Dexamethasone 4 mg/p.o. one day before dosing at Cycles 1 and 2 and 10 mg, i.v. at Day 1 before dosing and at Day 2 in Cycles 1 and 2. If a drug-related > grade 2 elevation of ALT and/or AST is observed
during the second cycle or thereafter, Dexamethasone pre-medication should be continued/re-introduced. In this case, Dexamethasone can be given orally on the day after the dosing day (Section 6.4.1).

Treatment Cycle	Screening	Cycle 1-3		Cycle 4-PD	End of Treatment	Unscheduled	
Day	-	1d	2d	8d	1d	-	
Before Infusion (on infusion days)	1	3	3 ^a	3	3	1	1 ^b
End of infusion (+15 minutes)		3			3		
End of infusion + 2 hours (± 15 minutes)		3					
End of infusion + 4 hours (± 30 minutes)		3					

Table 1-2 ECG Assessments in Dose Escalation Part – Applicable for Both Regimens

1 - Single ECG assessment

3 - Triplicate ECG assessments

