25 Repeat at least once more, i.e. on Day 5 if AST, ALT, or bilirubin > grade 1 and > 1.5×baseline.
²⁷ Only required at Cycles 1 and 2
²⁸ All patients must have a sample taken at Day 1 and 8 of Cycle 1 and at Day 8 of Cycle 3. If the visit occurs on an infusion day, the sample must be taken before IMP treatment.
$\frac{30}{10}$ Dexamethasone 4 mg/p.o. one day before dosing at Cycles 1 and 2 and 10 mg. i.v. at Day 1 before dosing and orally at Day 2 in Cycles 1 and 2. If a drug-related \geq grade 2 elevation of ALT and/or AST is
observed during the second cycle or thereafter, Dexamethasone pre-medication should be continued/re-introduced. In this case, Dexamethasone can be given orally on the day after the dosing day (Section

6.4.1).

³¹ If no AST, ALT, and/or bilirubin \geq grade 2 elevations are observed in Cycle 1 and 2, the visit at Cycle 3 Day 3 can be omitted.

Table 1-7 ECG Assessments in Expansion Part – Applicable for Both Regimens

Treatment Cycle	Screening	Cycle 1-3		Cycle 4-PD	End of Treatment	Unscheduled
Day	-	1d	8d	1d	-	
Before Infusion (on infusion days)	1	3	3	3	1	1 ^a
End of infusion (+15 minutes)		3		3		

1 – Single ECG assessment 3 – Triplicate ECG assessments

^a Optional.

Table 1-8 PK Sampling in Expansion Part – Applicable for Both Regimens

Treatment Cycle	Screening	Cycle 1-3		Cycle 4-PD	Unscheduled
Day/Week	-	1d	8d	1d	
Before Infusion (on infusion days)	X	Х	Х	Х	X^1
End of infusion (+15 minutes)		Х		Х	

¹ Optional.

Table 1-9 Vital Signs during the Expansion Part – Applicable for Both Regimens

Pre-infusion (up to 30 min before infusion)
At the end of infusion $(\pm 10 \text{min})^*$
1 hour after end of infusion (\pm 10 min)
2 hours after end of infusion (\pm 15 min)

*If infusion lasts for more than 60 minutes, vital signs should be assessed every 30 minutes (± 5 minutes) for the remaining duration of infusion.

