7.2.2 Mitigation Plan for Specific Adverse Events

7.2.2.1 Elevated Liver Parameters

All possibly IMP related events of elevated liver parameters must be managed as shown in Table 7-1 (except for DLTs that lead to permanent discontinuation of IMP).

Note: In case of a drug-related \geq grade 2 elevation of ALT and/or AST, pre-medication with dexamethasone must be administered to the patient upon subsequent dosings (see Section 6.4.1).

Table 7-1 Handling of Adverse Events Involving Elevated Liver Parameters

Baseline	Transaminases ^a		Bilirubin ^a	Action with IMP
G0-G1	G2: >3.0 - 5.0 x ULN	or	G2: >1.5 - 3.0 x ULN	Delay dosing ^{b, c}
G0-G1	G3: >5.0 - 20.0 x ULN	or	G3: >3.0 - 10.0 x ULN	Delay dosing ^{d, e}
G0-G1	G4: >20.0 x ULN	or	G4: >10.0 x ULN	Stop dosing
G0-G1	≥G2: >3.0 x ULN	and	>2.0 x ULN	Stop dosing ^f

Abbreviations: ALT = alanine aminotransferase, AST = aspartate aminotransferase, G = grade, ULN = upper limit of normal.

a Any AST, ALT, and / or bilirubin \geq grade 2 elevation needs to be checked 2x/week for up to 4 weeks.

b Re-start at same dose level at 1st occurrence when resolved to \leq grade 1 within 7 days / re-start at a reduced dose level at 2nd occurrence when resolved to \leq grade 1 within 7 days.

c Stop dosing at 3rd occurrence in case of unfavorable benefit-risk assessment by the DMC.

d Re-start at a reduced dose level, but only when resolved to \leq grade 1 within 7 days.

e Stop dosing at 2nd occurrence.

f Patients with ALT/AST>3.0 x ULN and bilirubin >2.0 x ULN with no signs of cholestasis, and for which the cause is at least possibly linked to study drug (i.e. a Hy's law case), must permanently discontinue trial drug.

- If a patient experiences AST, ALT or bilirubin elevations by more than one grade from baseline (grade 0→grade 2 as defined in the NCI-CTCAE Version 4.03), next dose of GEN1029 must be delayed until resolution to ≤ grade 1. Upon resolution to ≤ grade 1 within 7 days, treatment with GEN1029 may be re-started at same dose level for patients with 1st occurrence but at a reduced dose level (DL-1) for patients with 2nd occurrence. If requested by the investigator, the DMC and the sponsor may allow a patient with a favorable benefit-risk assessment to continue in the trial on a reduced dose even if the resolution to grade 1 occurs within 4 weeks. In case of 3rd occurrence a benefit-risk assessment GEN1029 therapy should be permanently discontinued.

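### Protocol sections 6.4.1 and 7.2.2.1 give different triggers for dexamethasone from cycle 3 on after a cycle-1 ALT/AST elevation, and should be reconciled

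*Protocol*

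**What the plan says.** Section 6.4.1 of the protocol fixes a mandatory window for dexamethasone, beginning with "4 mg/p.o. one day before dosing at Cycles 1 and 2" and followed by doses on Days 1 and 2 of the same two cycles. For later cycles it sets a condition, which applies to drug-related events at or above the grade named: "grade 2 elevation of ALT and/or AST is observed during the second cycle or thereafter, dexamethasone pre-medication should be continued/re-introduced".

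The two visit schedules carry the same condition. Table 1-1 footnote 33 (dose escalation) has "during the second cycle or thereafter, Dexamethasone pre-medication should be continued/re-introduced", and Table 1-6 footnote 30 (expansion) has "observed during the second cycle or thereafter, Dexamethasone pre-medication should be continued/re-introduced".

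The note near the start of section 7.2.2.1 concerns the same event, a drug-related ALT and/or AST elevation of grade 2 or higher, but names no cycle: "pre-medication with dexamethasone must be administered to the patient upon subsequent dosings". It then refers the reader to section 6.4.1.

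On timing, section 6.4.1 says of the elevations seen so far: "These elevations seem to be primarily a first-dose effect, and independent of dose level or presence of liver metastasis".

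**The concern.** The passages agree on the event (drug-related, ALT or AST, grade 2 or higher). They differ on which cycles' events count and on how binding the instruction is. The difference falls on a first-dose elevation, which is the timing the protocol treats as typical.

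Two things are at stake. The first is that a principal safety risk should be mitigated in the same way in every patient. The second is the reading of recurrences from cycle 3 on. Section 6.4.1 suggests that steroids may prevent these elevations, and Table 7-1 and section 7.3 attach consequences to repeat events: dose reduction at a second grade 2 occurrence, stopping at a second grade 3 occurrence, and a DMC benefit-risk assessment at a third rise of more than one grade. If later doses are covered in some patients and not in others who have the same history, those repeat events are harder to compare.

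**Working it through.** No sample size, power or error rate is involved, so the check sets the rules side by side by cycle of elevation and cycle of dosing. In every row the elevation is drug-related and of grade 2 or higher.

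| Elevation seen in | Next dosing in | 6.4.1 and the two footnotes | 7.2.2.1 note | Agree? |
|---|---|---|---|---|
| Cycle 1 | Cycle 2 | Required (mandatory window) | Required | Yes |
| Cycle 1 only | Cycle 3 or later | No requirement | Required | **No** |
| Cycle 2 or later | Any later cycle | *Should* | *Must* | Same trigger, different force |

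**Can a patient reach the second row?** Yes. Table 7-1 allows a restart after a first grade 2 elevation (same dose level) or a first grade 3 elevation (reduced dose level) when it resolves to grade 1 or lower within 7 days. In dose escalation, section 7.1 makes DLTs of grade 4 elevations, of grade 3 elevations that do not resolve to grade 1 or lower within 7 days, and of rises of more than one grade that do not so resolve. A DLT ends treatment, so those patients have no cycle 3. The second row therefore consists mainly of patients with short-lived cycle-1 elevations who stay on treatment.

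**Does it touch the DLT analysis?** The DLT period is 28 days, that is, cycles 1 and 2 (sections 4.3 and 7.1). Section 6.4.1 requires dexamethasone in both cycles and the 7.2.2.1 note removes none of it. The rules part only from cycle 3, so DLT counts, the mBOIN decisions and the MTD are not affected.

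**Can the affected patients be counted?** Section 6.4.1 reports elevations of grade 2 or higher in 11 of 24 Biweekly and 3 of 3 Intensified patients. The sums are consistent: 11 + 3 = 14 and 24 + 3 = 27, giving 14/27 = 51.9% overall and 11/24 = 45.8% Biweekly. Section 2.3 says that all three Intensified patients had DLTs from transaminase elevations, so they are not cases of this conflict. For the 11 Biweekly patients, the documents do not say how many events arose in cycle 1, how many were drug-related, or how many patients were dosed again in cycle 3. The 11 is a ceiling among those 24 at the 20-Aug-2019 cut-off, not an estimate. Mandatory dexamethasone dates only from Amendment 5 (18-Mar-2019), so these counts are not shown to be a rate under the present premedication rule.

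**The case against.** The strongest reply is that the texts do not strictly contradict each other. Section 6.4.1 sets a minimum and nowhere says to withhold dexamethasone from cycle 3 after a cycle-1 event. Section 7.2.2.1 is the plan for patients who have had an elevation, and a site that follows it satisfies both. That is logically correct, but it does not settle the matter. The 7.2.2.1 note sends the reader to 6.4.1, where the narrower trigger stands, and the schedule footnotes repeat that narrower trigger. One reader may take the cross-reference as importing the cycle limit; another may take it as pointing only to dose and route. Both readings are reasonable, and nothing else in the protocol or SAP decides between them.

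Other parts of the reply stand in full:

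- The expansion part was not initiated (SAP section 3), so Table 1-6 footnote 30 governed no patient.
- Mandatory cover ends after cycle 2 by design, so the by-cycle transaminase tables would mix covered and uncovered doses even if the passages agreed.
- The SAP already lists concomitant medication with dose, route and dates (section 14), and adverse events with cycle of onset and days since the latest dose (section 17.3). A display that joins the two is a convenience, not a missing analysis.

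A reader might infer that sites did in fact premedicate patients differently. The documents show only that they could. A reader might also take the 51.9% or 45.8% above as the share affected; neither figure counts patients who had a cycle-1 event and were dosed in cycle 3 or later.

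**Conclusion.** The inconsistency is real and limited. For one defined group (a drug-related ALT/AST elevation of grade 2 or higher in cycle 1 only, no discontinuation for a DLT, dosing in cycle 3 or later) section 6.4.1 and the schedule footnotes require nothing, while section 7.2.2.1 mandates premedication. For elevations in cycle 2 or later the trigger is the same and only the force differs. The size of the group cannot be computed from the documents, and the primary endpoint is untouched.

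The point matters because the protocol places these elevations mainly at the first dose, and because recurrence drives dose reduction and stopping. It rests on reading the 7.2.2.1 note as written, with no cycle limit. If the sponsor meant the cross-reference to carry that limit over, the note needs to say so.

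**What to change.** The sponsor and the DMC should reconcile section 6.4.1, Table 1-1 footnote 33, Table 1-6 footnote 30 and the note in section 7.2.2.1. All four should state one trigger (which cycles' elevations count) and one level of obligation. This review does not say which rule is right. The cost is wording in four places and a notice to sites, with no added visits or samples. The Table 1-6 edit is for document consistency only.

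Optionally, for the escalation data, show beside SAP Table 14.03.16.05 whether dexamethasone was given (yes/no) at each dose after a patient's first drug-related ALT/AST elevation of grade 2 or higher. Section 6.4.1 already requires all premedication to be recorded on the concomitant medication page, so this costs one listing programmed from existing data. It would let a reader see whether later recurrences arose with or without steroid cover.
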